6.1.1. Screening Period

Once informed consent has been obtained, subjects will be screened over a period of 3 days prior to Baseline for study eligibility determination, medical history review and demographic data collection. Every attempt will be made to minimize this 3 day period, and subjects may have their Screening and Baseline visits on the same date. Assessments required for Screening and/or eligibility determination will also include the following: acute GVHD staging (at the Screening visit; staging at the time of diagnosis, that can occur up to 7 days prior of the first dose of ALXN1007, will also be recorded), physical exam (including height), vital signs, weight, *C. difficile* stool test, laboratory tests, endoscopy of upper and/or lower GI tract with biopsy, pregnancy test (for women of childbearing potential), and recording of AEs (see Section 11.2), prior and concomitant medications and therapies, and information on HCT performed, including conditioning regimen and post-transplant GVHD prophylaxis regimen (see Section 8.2). Results of evaluations performed as part of "standard of care" prior to informed consent are allowed for *C. difficile* testing and endoscopic biopsy.

6.1.1.1. Biopsy

A biopsy of the upper and/or lower GI tract performed within 7 days of screening can be used to determine eligibility. Biopsy results may not be available until after the first treatment visit. If GI GVHD is not confirmed histologically, study treatment will be discontinued and an ET visit should be completed 6 weeks after the last dose of ALXN1007 was received. Subjects should continue antibiotic prophylaxis for 6 weeks after the last dose of ALXN1007 (see Section 6.1.1.3).

All biopsy specimens will be reviewed by both the Investigator's local pathology lab, as well as The University of Texas MD Anderson Cancer Center laboratory, which will serve as the central pathology laboratory for this study. Any discrepancies in biopsy interpretation between the central pathology laboratory and the Investigator's local pathology laboratory will be resolved by the Alexion Medical Monitor and the Investigator to determine if study treatment should continue.

6.1.1.2. GVHD Staging

Staging will be collected at all time points indicated in the Schedule of Events (including at Screening and Baseline; refer to Table 3 and Table 4). In addition, the stage at the time of diagnosis, that can occur up to 7 days prior of the first dose of ALXN1007, will also be recorded and will be used 1) to determine study eligibility and 2) for comparison to post-Baseline GVHD staging to assess treatment response to ALXN1007 in combination with corticosteroids. Acute GVHD staging will be performed using the Modified Keystone Grading Schema (Table 10 and Appendix 1), which includes skin, liver and lower GI assessments. Lower GI assessment consists of determination of stool volume over a 24-hour period. Detailed instructions for determining stool volume can be found in the study operations manual (SOM) for the study.

6.1.1.3. Antibiotic Prophylaxis

Subjects must continue or begin antibiotic prophylaxis active against meningococcal infection prior to receiving the first dose of ALXN1007. Subjects already receiving empirical antibiotic prophylaxis for bacterial infections or therapeutic antibiotic treatment must be receiving an

antibiotic throughout the treatment period and for 6 weeks after the last dose of ALXN1007 that is active against encapsulated organisms (including *Neisseria meningitidis*) based on institutional guidelines. If patients are receiving prophylactic, empirical or therapeutic antibiotic treatment with drugs that have activity against meningococcus (and pneumococcus), no additional antibiotic prophylaxis will be required during that treatment period.

6.1.2. Treatment Period (Baseline - Day 56)

The first dosing cohort (Cohort 1) will receive 10 mg/kg ALXN1007 administered IV QW for 8 weeks. With approval of Amendment 6, Cohort 2, 20 mg/kg QW for 8 weeks, will be added to the study. An additional cohort, 20 mg/kg twice weekly for 8 weeks (Cohort 3), is planned after DMC review of safety and tolerability data at Day 28 on the first 3 patients in Cohort 2. At the discretion of the Sponsor, and in consultation with the DMC, other dosing cohorts (not to exceed a total dose of 40 mg/kg per week for 8 weeks) may also be explored as described in Section 6.3.

Review of biopsy histology for confirmation of GI GVHD will occur when biopsy results are available. For subjects without histologically confirmed GI GVHD, refer to Section 6.1.5 for guidance on discontinuing ALXN1007 treatment and conducting an ET visit.

The first ALXN1007 dose will be administered at Baseline. Following this, subjects will receive once weekly dosing until Day 49, or twice weekly dosing until Day 52 (if twice weekly dosing schedule is being administered). On Day 56, subjects will undergo follow-up evaluations but will not receive ALXN1007 treatment.

Each visit during the Treatment Period (including Day 56) should occur at the day indicated \pm 2 days (if the subject is on a weekly dosing schedule) or \pm 1 day (if the subject is on a twice weekly dosing schedule). For subjects on a weekly dosing schedule, there should be a minimum of 4 days between ALXN1007 doses. For subjects on a twice weekly dosing schedule, there should be a minimum of 2 days between ALXN1007 doses. If the recommended acceptable windows cannot be observed, the Sponsor or its representative must be contacted prior to scheduling a visit.

All doses of ALXN1007 will be administered as a continuous IV infusion. Subjects will remain under observation for 2 hours after the infusion. Refer to Sections 9.4 and 9.5, as well as the Pharmacy Manual, for procedures pertaining to the preparation and administration of ALXN1007.

6.1.2.1. Baseline

Prior to Infusion of ALXN1007

Baseline evaluations will include the following: acute GVHD staging, ECG, vital signs, weight, laboratory tests, including any monitoring of anti-rejection drugs, if applicable, pregnancy test (for women of childbearing potential) (note: if the Baseline visit is within 24 hours of Screening, the pregnancy test does not need to be repeated), PK/PD (collected within 4 hours prior to the start of infusion [SOI]), antibodies to ALXN1007, exploratory biomarkers, optional PGx (if consent has been provided), recording of AEs (see Section 11.2) and concomitant medications and therapies (see Section 8.2).

The Investigator or designee must confirm that the subject is receiving antibiotic prophylaxis active against meningococcal infection prior to receiving the first dose of ALXN1007.

Administration of ALXN1007

All doses of ALXN1007 will be administered as a continuous IV infusion. Subjects will remain under observation during and for 2 hours after the infusion. Refer to Sections 9.4 and 9.5 and the Pharmacy Manual for procedures pertaining to the preparation and administration of ALXN1007.

Post Infusion of ALXN1007

Blood samples for PK/PD will be collected at the end of infusion (EOI) plus 3 hours post-SOI. If the subject is hospitalized, then PK/PD samples will also be collected 5 hr, 24 hr, 48 hr and 72 hr post-SOI (for subjects on a weekly ALXN1007 dosing schedule) or 5 hr, 24 hr and 48 hr post-SOI (for subjects on a twice weekly ALXN1007 dosing schedule). End of infusion time point has a collection window of \pm 5 minutes; 3 and 5 hour post SOI time points have a window for collection of \pm 15 minutes; and 24, 48 and 72 hour time points have a window for collection of \pm 2 hours.

An ECG will also be done at EOI.

Subjects will remain under observation for 2 hours after the infusion.

6.1.2.2. Days 3-56

The evaluations that will occur during the remainder of the Treatment Period include the following: acute GVHD staging (Days 7, 14, 21, 28, 35, 42, 49, and 56), physical exam (Days 28 and 56 only), ECG (pre and post dose on Day 28, and once on Day 56), vital signs (all visits), weight (Days 7, 14, 21, 28, 35, 42, 49, and 56), laboratory tests (Days 7, 14, 21, 28, 35, 42, 49 [for subjects on a weekly dosing schedule] or 52 [for subjects on a twice weekly dosing schedule], and 56 [for subjects on a weekly dosing schedule]), pregnancy test (urine or serum, for women of childbearing potential) (Days 7, 14, 21, 28, 35, 42, 49, and 56), antibodies to ALXN1007 (Days 7, 28 and 56), exploratory biomarkers (Days 7, 28 and 49), and recording of AEs (see Section 11.2) and concomitant medications and therapies (see Section 8.2).

Samples for PK/PD assessment will also be collected during this same time period. A summary of study visits (and time points) for PK/PD sample collection can be found in Table 5 (see also Table 3 and Table 4).

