^{*} Screening period for the study will be initiated after informed consent form signing (ie, subject enrollment). Acute GI GVHD staging at the time of diagnosis (that can be made up to 7 days prior to the first ALXN1007 dose) will be captured and used for comparison to post-Baseline GVHD staging to assess treatment response.

^{**} With approval of Amendment 6, Cohort 2 (20 mg/kg QW for 8 weeks) will be added to the study. An additional cohort (Cohort 3, 20 mg/kg twice weekly for 8 weeks), is planned after DMC review of safety and tolerability data at Day 28 on the first 3 patients in Cohort 2. At the discretion of the Sponsor, and in consultation with the DMC, other dosing cohorts (not to exceed a total dose of 40 mg/kg per week for 8 weeks) may also be explored based on cumulating safety and tolerability data as well as any PK/PD data that may be available.

^{***} Follow-up period for the study consists of study visits at Weeks 12 (Day 86) and 26 (Day 180), with telephone contact at Week 52 (Day 360) for survival status only.

Table 3: Schedule of Events for Subjects on a Once Weekly ALXN1007 Dosing Schedule

Procedures and Evaluations	Screening	Treatment (± 2 days)										Follow-up (± 15 days, except for ET)			
Weeks		0	1	2	3	4	5	6	7	8	12	26		52	
Days	-3 to -1	Baseline	7	14	21	28	35	42	49	56	86	180	ET	360	
Informed Consent	X														
Eligibility - Inclusion/Exclusion Criteria	X	X^1													
Medical History, Demographics	X														
ALXN1007 Administration ²		X	X	X	X	X	X	X	X						
Acute GVHD Staging ³	X	X	X	X	X	X	X	X	X	X	X	X	X		
Antibiotic Prophylaxis Against Meningococcal Infection ⁴	X	X	X	X	X	X	X	X	X	X	X ⁴		X ⁴		
Physical Exam ⁵	X					X				X		X	X		
ECG		X^6				X^6				X		X	X		
Vital Signs ⁷	X	X	X	X	X	X	X	X	X	X	X	X	X		
Weight	X	X	X	X	X	X	X	X	X	X	X	X	X		
Stool Clostridium difficile Testing (Local lab)	X														
CSA, Tacrolimus, and/or Sirolimus Levels (if needed) ⁸		X	X		X		Х		X				X		
CMV-PCR		X	X	X	X	X	X	X	X	X			X		
Routine Laboratory Test ⁹	X	X	X	X	X	X	X	X	X	X	X	X	X		
Creatinine Clearance (local lab)	X														
ANC (local lab)	X														
Endoscopy of Upper and/or Lower GI Tract / Biopsy ¹	X														
CPK, Thyroid Function Tests (Central lab)		X	X			X				X	X	X	X		

Table 3: Schedule of Events (Continued)

Procedures and Evaluations	Screening		Treatment (± 2 days)							Follow-up (± 15 days, except for ET)				
Days	-3 to -1	to -1 Baseline 7 14 21 28 35 42 49 56	56	86	180	ET	360							

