- ¹²On all dosing days, samples will be collected within 4 hours prior to the start of infusion (SOI). If positive for antibodies to ALXN1007 on Day 180 or the ET visit, the subject may be followed every 3 months until negative or stabilized, based on the measured titer and the safety assessments in that specific subject.
- ¹³On all dosing days, samples will be collected within 4 hours prior to the SOI.
- ¹⁴To participate in this optional PGx portion of the study, subjects must also sign the pharmacogenetic informed consent document.
- ¹⁵ All AEs will be recorded from the signing of informed consent until 30 days after the last dose of ALXN1007. All SAEs will be recorded from signing of informed consent through the Day 180 visit. In addition, any notifications of death as a result of the Day 360 survival follow-up will also be recorded; the cause of death or event leading to death should be reported as an SAE. Note: There is no time limit for reporting SAEs that are considered causally related.

Table 4: Schedule of Events for Subjects on Twice Weekly ALXN1007 Dosing Schedule

Procedures and Evaluations	Screening							Trea	tment	Period	(± 1 d	ay)							Fo	Follow-up (± 15 days, except for ET)			
Weeks		0			1	:	2	:	3	4	4	:	5		6		7	8	12	26		52	
Days	-3 to -1	Baseline	3	7	10	14	17	21	24	28	31	35	38	42	45	49	52	56	86	180	ET	360	
Informed Consent	X																						
Eligibility - Inclusion/Exclusion Criteria	X	X^1																					
Medical History, Demographics	X																						
ALXN1007 Administration ²		X	X	X	X	X	X	X	X	X	X	X	X	X	X	X	X						
Acute GVHD Staging ³	X	X		X		X		X		X		X		X		X		X	X	X	X		
Antibiotic Prophylaxis Against Meningococcal Infection ⁴	X	X		X		X		X		X		X		X		X		X	X ⁴		X ⁴		
Physical Exam ⁵	X									X								X		X	X		
ECG		X^6								X^6								X		X	X		
Vital Signs ⁷	X	X	X	X	X	X	X	X	X	X	X	X	X	X	X	X	X	X	X	X	X		
Weight	X	X		X		X		X		X		X		X		X		X	X	X	X		
Stool Clostridium difficile Testing (Local lab)	X																						
CSA, Tacrolimus, and/or Sirolimus Levels (if needed) ⁸		X		X				X				X				X					X		
CMV-PCR		X		X		X		X		X		X		X		X		X			X		
Routine Laboratory Test ⁹	X	X		X		X		X		X		X		X			X		X	X	X		
Creatinine Clearance (local lab)	X																						
ANC (local lab)	X																						
Endoscopy of Upper and/or Lower GI Tract / Biopsy ¹	X																						
CPK, Thyroid Function Tests (Central lab)		X		X						X								X	X	X	X		

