- ³ Acute GVHD staging includes skin, liver and GI assessments, which will be performed using the Modified Keystone Grading Schema. Lower GI tract assessment consists of determination of stool volume over a 24-hour period. Detailed instructions for determining stool volume can be found in the study operations manual (SOM) for the study. Staging will be collected at all time points indicated in the Schedule of Events (including at Screening and Baseline). In addition, the stage at the time of diagnosis, that can occur up to 7 days prior of the first dose of ALXN1007, will also be recorded and will be used 1) to determine study eligibility and 2) for comparison to post-Baseline GVHD staging to assess treatment response to ALXN1007 in combination with corticosteroids.
- ⁴ Subjects must continue or begin antibiotic prophylaxis active against meningococcal infection prior to receiving the first dose of ALXN1007. Subjects already receiving empirical antibiotic prophylaxis for bacterial infections or therapeutic antibiotic treatment must be receiving an antibiotic throughout the treatment period and for 6 weeks after the last dose of ALXN1007 that is active against encapsulated organisms (including Neisseria meningitidis) based on institutional guidelines. If patients are receiving prophylactic, empirical or therapeutic antibiotic treatment with drugs that have activity against meningococcus (and pneumococcus) no additional antibiotic prophylaxis will be required during that treatment period.

⁵ Height measurement at Screening only.

⁶ ECG to be performed pre-dose and at end of infusion (EOI).

⁷ Vital Signs: BP, pulse, temperature and respiratory rate. Vital signs will be obtained after the subject has been supine or seated for at least 5 minutes.

The timing of sample collection (eg, trough) should be appropriate for the drug being monitored and not coupled with the timing of administration of ALXN1007.

⁹ Screening labs should be done at local lab; Baseline through end of study assessments are to be done at central lab.

¹⁰ Serum pregnancy test at Screening only (local lab); serum or urine dipstick pregnancy tests thereafter (local lab). For women of childbearing potential only. If Baseline is within 24 hours of the Screening pregnancy test, it does not need to be repeated.

¹¹Refer to Table 5 for required time points for PK/PD sample collection time points by visit.

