8.2.2. Immunosuppressive Medications

GVHD prophylaxis should be based on institutional practice. Subjects developing acute GVHD during GVHD prophylaxis (ie, while on calcineurin inhibitors, sirolimus, etc) should have their prophylaxis medication continued during the study period unless discontinuation is clinically indicated (eg, for management of toxicity). Medications such as cyclosporine (CSA), tacrolimus or sirolimus (if used as GVHD prophylaxis when acute GVHD developed) should be continued at therapeutic doses and adjusted as necessary for renal, central nervous system or other toxicity using conventional management guidelines. The recommended therapeutic trough level of CSA is 200-400 ng/mL measured by whole blood high-performance liquid chromatography (HPLC), and institutional levels for other assays. The recommended therapeutic trough level is 5-15 ng/mL for tacrolimus and 3-12 ng/mL for sirolimus.

Subjects may be switched to an alternate immunosuppressive regimen as clinically indicated or based on side effects at the discretion of the Investigator. Dose adjustments for CSA should be

made based on serum bilirubin and creatinine. As applicable, drug levels of CSA, tacrolimus and sirolimus should be obtained at Baseline and on dosing on Days 7, 21, 35 and 49, as well as the ET visit. The timing of sample collection (eg, trough) should be appropriate for the drug being monitored and not coupled with the timing of administration of ALXN1007. This will be done for monitoring and dose adjustment per standard of care, or more frequently as needed. These immunosuppressants may result in a variety of drug interactions, which may require dose adjustments:

- Cyclosporine (CSA): Dosing should follow institutional practice with typical regimens consisting of initial IV CSA dose followed by tapering and then oral dosing with tapering.
- **Tacrolimus:** Dosing should follow institutional practice with typical regimens consisting of initial IV tacrolimus dose followed by tapering and then oral dosing with tapering.
- **Sirolimus:** Dosing should follow institutional practice with typical regimens consisting of an oral loading dose followed by tapering.
- **Mycophenolate mofetil:** Dosing should follow institutional practice with typical regimens consisting of oral dosing.
- Intravenous immunoglobulin (IVIG): Dosing should follow institutional practice.

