11.1.7. Laboratory Assessments

Subjects will have blood samples collected for routine laboratory tests that include: analysis of chemistry panel, coagulation panel, and CBC with differential and platelets at every study visit (Appendix 3).

Urinalysis will be conducted at Screening, Baseline, Days 28, 56 and 180, as well as at the ET visit if a subject prematurely discontinues or is withdrawn from the study.

Local labs may be used to assess ANC, C. difficile, serum (or urine) pregnancy, and CrCl.

For women of childbearing potential, a serum pregnancy test will be performed at Screening, and a urine pregnancy test will be performed at Baseline (if more than 24 hours from the Screening pregnancy test) and Days 7, 14, 21, 28, 35, 42, 49, 56, 86 and 180, as well as at the ET visit if a subject prematurely discontinues or is withdrawn from the study. At the Investigator's discretion, serum pregnancy tests may be done in place of urine pregnancy tests.

Blood samples for creatine phosphokinase (CPK) and thyroid function tests (thyroid peroxidase antibody [TPO], thyroid-stimulating hormone [TSH], and free thyroxine [FT-4]) will be collected at Baseline and on Days 7, 28, 56, 86 and 180, as well as at the ET visit if a subject prematurely discontinues or is withdrawn from the study.

As applicable, levels of CSA, tacrolimus and/or sirolimus will be determined at Baseline and on Days 7, 21, 35 and 49, as well as at the ET visit if a subject prematurely discontinues or is withdrawn from the study. The timing of sample collection (eg, trough) should be appropriate for the drug being monitored and not coupled with the timing of administration of ALXN1007.

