APPENDIX 1. MODIFIED KEYSTONE GRADING SCHEMA

Modified Keystone Grading Schema

	Stage 0	Stage 1	Stage 2	Stage 3	Stage 4
Skin	No Rash	Rash <25%	25-50%	>50%	Bullae and
		BSA	BSA	BSA	desquamation
Lower	<500 ml/day	500-	1001-	>1500 ml/ day	Severe
GI Tract	stool volume	1000 ml/day	1500 ml/day	stool volume	abdominal pain
1		stool volume	stool volume		+/- ileus, frank
					blood or melena
Liver ²	≤2 mg/dl	2.1-3 mg/dl	3.1-6 mg/dl	6.1-15 mg/dl	>15 mg/dl

Abbreviations: BSA = body surface area; GI = gastrointestinal (Przepiorka, 1995)

¹ Lower GI tract assessment consists of determination of stool volume over a 24-hour period. Detailed instructions for determining stool volume can be found in the Study Operations Manual (SOM) for the study.

² Values presented for each stage are bilirubin level.

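### Twice-weekly (Cohort 3) subjects are staged for liver GVHD at Days 49 and 56 with no routine panel, hence no bilirubin, scheduled at either visit, although Protocol 11.1.7 has the panel at every visit

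*Protocol*

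**What the plan says.** Protocol 6.1.2.2 lists staging for both dosing schedules as "acute GVHD staging (Days 7, 14, 21, 28, 35, 42, 49, and 56". For laboratory tests it separates the schedules after Day 42: weekly subjects have Days 49 and 56, and twice-weekly subjects have Day 52 ("or 52 [for subjects on a twice weekly dosing schedule], and 56 [for subjects on a weekly dosing schedule"). Table 4 ("Schedule of Events for Subjects on Twice Weekly ALXN1007 Dosing Schedule") shows the same pattern. Its routine laboratory row is marked at Day 52 and blank at Days 49 and 56; its staging row is marked at Days 49 and 56 and blank at Day 52. Table 3 ("Schedule of Events for Subjects on a Once Weekly ALXN1007 Dosing Schedule") has the panel at every staging visit.

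Protocol 11.1.7 makes no distinction by schedule. It describes routine tests as "analysis of chemistry panel, coagulation panel, and CBC with differential and platelets at every study visit".

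Footnote 3 of Table 4 requires the liver at each staging: "Acute GVHD staging includes skin, liver and GI assessments, which will be performed using the Modified Keystone Grading Schema". Appendix 1 says of the liver row, "Values presented for each stage are bilirubin level". Total bilirubin appears in the chemistry panel of Appendix 3.

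Protocol 5.2.2 lists all-organ response at Days 14, 28 and 56. SAP 7.2.2.1 still tabulates GI and all-organ response at all visits, observed and imputed. Under SAP 5.1.2.2, all-organ complete response needs stage 0 in every organ.

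**The concern.** The twice-weekly schedule asks for a liver stage at two visits without scheduling the one measurement that defines it. Day 56 is the more important of the two, because all-organ response at Day 56 is a listed endpoint that survives into the abbreviated analysis. Without a bilirubin, complete response cannot be established, and liver worsening cannot be ruled out.

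The GI-specific categories are also touched. Under SAP 5.1.2.1, a GI improvement becomes a mixed response if another organ has deteriorated, so the liver stage enters the by-visit GI tables at Days 49 and 56.

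The SAP appears to analyse the stages as recorded. Whatever the site enters for the liver would be used as it stands. The staging listing in SAP 7.2.2.1.1 is titled for stage score, rash area and stool volume, so it would not show which bilirubin a Cohort 3 liver stage came from.

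**Working it through.** The plan gives no figure to reproduce. The check sets the visit schedules side by side.

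**Inputs.** Staging and routine laboratory rows of Tables 3 and 4, read cell by cell; the Table 4 rows have 22 cells for 22 day columns. Visit windows are from Protocol 6.1.2 (±1 day for twice-weekly treatment visits).

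| | Table 3 (weekly) | Table 4 (twice weekly) |
|---|---|---|
| Staging | Screening, Baseline, 7, 14, 21, 28, 35, 42, 49, 56, 86, 180, ET (13) | the same 13 visits |
| Routine panel | the same 13 visits | Screening, Baseline, 7, 14, 21, 28, 35, 42, 52, 86, 180, ET (12) |
| Staging with same-visit panel | 13 of 13 | 11 of 13 |
| Staging without panel | none | Days 49 and 56 |
| Panel without staging | none | Day 52 |

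Table 4 and the text of 6.1.2.2 give the same days, so the blank cells are unlikely to be a fault of text extraction.

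**Against 11.1.7.** Table 4 has no panel at Days 3, 10, 17, 24, 31, 38, 45, 49 and 56. The conflict with the every-visit wording therefore extends to the mid-week visits, but only Days 49 and 56 also require staging.

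**Distance to the nearest panels.**
- Day 56 staging, previous panel at Day 52: 56 − 52 = 4 days. With windows, 55 − 53 = 2 to 57 − 51 = 6 days. The next panel is at Day 86.
- Day 49 staging, previous panel at Day 42: 49 − 42 = 7 days, range 48 − 43 = 5 to 50 − 41 = 9. Next panel at Day 52: 52 − 49 = 3 days, range 51 − 50 = 1 to 53 − 48 = 5.
- Last staging visit before Day 56 that has its own panel is Day 42: 56 − 42 = 14 days, range 55 − 43 = 12 to 57 − 41 = 16.

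**Endpoints touched.** Of the listed all-organ timepoints {14, 28, 56}, only Day 56 lacks a same-visit panel: 1 of 3. Day 28 has a panel, so the primary endpoint is unaffected. Day 49 is not a listed response timepoint but is included in the SAP's all-visit summaries.

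**Other scheduled sources of bilirubin.** Protocol 8.2.2 says that cyclosporine dose adjustments should be "made based on serum bilirubin and creatinine". This concerns cyclosporine-treated subjects only. Scheduled drug levels in Table 4 fall at Baseline, Days 7, 21, 35 and 49 and ET, so Day 56 is not among them; in any case, the section does not tie bilirubin draws to those days. The laboratory footnote to Table 4 assigns tests from Baseline onward to the central laboratory, and bilirubin is not in the list of local tests in 11.1.7. Neither document names a routine-care value as the source for staging.

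**The case against.** The strongest reply is that staging is a required procedure in its own right. A site cannot complete it without a bilirubin, and neither document says that the bilirubin must come from the routine panel. The stage at diagnosis may itself predate any study panel (Protocol 6.1.1.2), so outside values are already part of the design. This stands as far as it goes: a same-visit routine-care value is plausible in these patients and would support a valid stage. But it is neither scheduled nor designated, so its presence at Day 56 is left to chance.

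A second reply is that if sites followed 11.1.7, the panel would have been drawn. That is true, and it is why the effect on data is conditional. It does not remove the contradiction.

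A third is that SAP 7.2.2.1 already has rules for missing responses. Those rules deal with missed visits, discontinuation and death. They give no instruction for a visit with skin and gut staged but liver unknown. Carrying forward would also reach back to Day 49, which has the same gap.

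A fourth is that SAP 4.1 promises by-patient listings of all data, so study bilirubin dates can be compared with recorded stages. This is correct for panel values. A routine-care bilirubin could be traced only if it was collected.

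Finally, the cohort is tiny, no hypothesis is tested, and the study ended early. All of this is accepted. It limits the weight of the point but does not refute it.

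**Conclusion.** The concern holds. Table 4 and Protocol 6.1.2.2 contradict 11.1.7 and, unlike Table 3, leave two of 13 staging visits without a scheduled bilirubin. The consequence for data depends on sites having worked to Table 4 and on no routine-care bilirubin having been available on the day.

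The size is small: one cohort of 3 to about 6 planned subjects, one of three listed all-organ timepoints, and descriptive analysis only. The documents do not say how many Cohort 3 subjects reached Day 56 or had a bilirubin that day. The number affected may be 0, or it may be every Day 56 all-organ result in the planned cohort with the highest weekly dose. Neither the primary result nor the Day 14 and Day 28 all-organ results are in doubt. It should be corrected because the remedy is cheap.

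**What to change.** 1. Reconcile Table 4, Protocol 6.1.2.2 and Protocol 11.1.7. For the staging endpoint, schedule the routine panel, or at minimum total bilirubin, at the Day 49 and Day 56 staging visits for twice-weekly subjects, leave Day 52 as it is, and make the wording of 11.1.7 match Tables 3 and 4.
2. For data already collected, footnote any Cohort 3 response at Day 49 or Day 56 whose liver stage does not rest on a same-visit bilirubin.

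The first item is a table and wording correction plus an added test at two visits where blood is already drawn (Day 49: CMV-PCR, PK/PD, biomarkers; Day 56: CMV-PCR, CPK and thyroid tests, PK/PD, antibodies). Because the study ended early, the footnote is the part that applies to the collected data. It requires checking stage dates against bilirubin dates in one small cohort and no new procedures.
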